#### **5.4** Supportive Care

Subjects should receive full supportive care in accordance with ASCO or equivalent guidelines on supportive care for solid tumors, if necessary. Supportive care measures may include but are not limited to anti-diarrheal agents, anti-emetic agents, opiate and non-opiate analgesic agents, appetite stimulants, and granulocyte and erythroid growth factors. Subjects will receive supportive care as judged by their treating physician. If it is unclear whether a therapy should be regarded as supportive care, the site investigator should consult with HCRN. Use of any supportive care therapy should be reported on the eCRFs.

# 5.4.1 Analgesic agents

The use of analgesic agents during the study is permitted at the discretion of the site investigator. The subject is receiving chronic antiplatelet therapy, including aspirin, nonsteroidal anti-inflammatory drugs (NSAIDs, including ibuprofen, naproxen, and others), dipyridamole or clopidogrel, or similar agents will be excluded. Once-daily aspirin use (maximum dose 325 mg/day) is permitted. Chronic use of analgesic agents with no or low bleeding risk (for example acetaminophen) is acceptable. See exclusion criteria above for additional information.

# 5.4.2 Antiemetic therapy

The use of antiemetic agents is permitted during this study and at the discretion of the site investigator. However, it is recommended to follow the guidelines of the Multinational Association of Supportive Care in Cancer (MASCC) and ASCO.

# **5.4.3** Appetite Stimulants

The use of appetite stimulants is permitted at the discretion of the site investigator.

#### **5.4.4** Blood Product Transfusions

Transfusions of red blood cells, platelets or other blood products are permitted at the site investigators discretion during the conduct of the study.

#### 5.4.5 Treatment of Diarrhea

In the event of diarrhea, the following supportive measures are strongly recommended:

Subjects should be advised to drink at least 3 L of fluids per day. Frequent small meals are recommended.

Upon the subject experiencing the first episode of a loose stool, the subject should take an initial dose of loperamide 2 capsules (4 mg) by mouth, then I capsule (2 mg) by mouth every 2 hours or 2 capsules every 4 hours overnight for at least 12 hours after the first liquid stool and up to 12 hours after the last liquid stool without exceeding total treatment duration of 48 hours.

For uncomplicated Grade 1 or 2 diarrhea that does not resolve after 24 hours, start a broad spectrum antibiotic such as a fluoroquinolone for a 7-day course. After 48 hours of unresolved uncomplicated Grade 1 or 2 diarrhea the subject should stop loperamide and be evaluated in the out subject setting with a stool workup, complete blood count (CBC) and

Version Date: 13AUG2018 Confidential Page 17 of 51

replacement of fluids and electrolytes as clinically indicated. A second-line agent, such as octreotide, should then be considered.

Octreotide has been shown to be effective in the control of diarrhea induced by fluoropyrimidine-based chemotherapy regimens when administered as an escalating dose by continuous infusion or subcutaneous injection. Octreotide can be administered at doses starting from 100 mcg 3 times daily and escalating to 500 mcg 3 times daily.

Subjects should be admitted to the hospital whenever they present with Grade 3 or 4 diarrhea, or when they have complicated Grade 1 or 2 diarrhea, defined as having diarrhea *plus* one or more of the following symptoms: cramping, nausea/vomiting grade  $\geq$  2, decreased performance status, fever, sepsis, neutropenia, frank bleeding or dehydration. If the subject is already on loperamide, it should be stopped, and the subject should be started on octreotide, intravenous fluids and undergo a stool workup CBC and electrolyte evaluation, with repletion as clinically indicated. In addition, if the subject is febrile or has an ANC  $\leq$  500 a broad-spectrum antibiotic should be started for at least 7 days and until the resolution of fever and an ANC  $\geq$  1000. Events that require a subject to be hospitalized are considered SAEs.

It is imperative that subjects have access to loperamide for home use prior to the start of each cycle. In addition, subjects should receive oral and written information about the risk for diarrhea, associated symptoms and instructions on how to manage diarrhea. This includes the need for oral hydration, when and how to take medications, when to notify the site physician and when to report to the hospital for further treatment. These recommendations have been adapted from the ASCO guidelines (Benson et al. 2004)

# **5.4.6** Erythroid Growth Factors

The use of erythroid-stimulating factors is permitted at the discretion of the site investigator based on ASCO and FDA guidelines (FDA 2009; Rizzo et al.2010) or according to local guidelines.

# 5.4.7 Therapy for Febrile Neutropenia

Subjects experiencing febrile neutropenia, especially with diarrhea or dyspnea, should be managed in a hospital setting according to standard procedures, with the urgent initiation of intravenous antibiotic therapy.

#### **5.4.8** Granulocyte Colony-Stimulating Factors

The use of granulocyte-colony stimulating factor (G-CSF) or similar agents is permitted during this study, at the discretion of the site investigator based on local guidelines or ASCO (Smith et al. 2006), European Society for Medical Oncology (Crawford et al. 2009). Note that prophylactic use of G-CSF or similar agents is also permitted.

#### **5.4.9 Hand-Foot Syndrome**

Also called palmar-plantar erythrodysesthesia is a side effect of some types of chemotherapy. Treatment with pyridoxine (B6) at a dose of 100 to 150 mg per day is allowed.

Version Date: 13AUG2018 Confidential Page 18 of 51

#### **5.4.10** Hypersensitivity Reactions

Premedication for ramucirumab/placebo administration: H1 antagonist (for example, diphenhydramine hydrochloride) intravenously. Additional premedication and treatment may be provided at site investigator discretion. All premedication administered must be adequately documented in the eCRF.

Premedication after first episode of grade 1 or 2 infusion-related reaction: Subjects should be premedicated within 30 minutes prior to infusion with antihistamines, corticosteroids, acetaminophen, etc.

Treatment for second episode of grade 1 or 2 infusion-related reaction: administer dexamethasone 8 to 10 mg I.V. (or equivalent). For subsequent infusions pre-medicate with diphenhydramine hydrochloride 50 mg I.V. (or equivalent), acetaminophen 650 mg orally and dexamethasone 8 to 10 mg I.V. (or equivalent). Reduce the ramucirumab infusion rate by 50% for the duration of the infusion and all subsequent infusions if the patient experiences a Grade 1 or 2 IRR (per NCI-CTCAE).

Treatment for grade 3 or 4 infusion-related reaction: Subjects should be treated with epinephrine, bronchodilators and/or glucocorticoids for symptomatic bronchospasm and I.V. fluids and/or pressors for hypotension. Subjects with grade 3 or 4 infusion reaction must not receive further treatment with ramucirumab.

# 5.4.11 Contraception

Ramucirumab may have adverse effects on a fetus in utero. Furthermore, it is not known if ramucirumab has transient adverse effects on the composition of sperm. Subjects should start using birth control from time of consent throughout the study period up to 90 days after the last dose of study therapy.

The following are considered adequate barrier methods of contraception: diaphragm, condom (by the partner), copper intrauterine device, sponge, or spermicide. Appropriate hormonal contraceptives will include any registered and marketed contraceptive agent that contains an estrogen and/or a progestational agent (including oral, subcutaneous, intrauterine, or intramuscular agents).

Subjects should be informed that taking the study medication may involve unknown risks to the fetus (unborn baby) if pregnancy were to occur during the study. In order to participate in the study, they must adhere to the contraception requirement (described above) for the duration of the study and during the follow-up period. If there is any question that a subject will not reliably comply with the requirements for contraception, that subject should not be entered into the study.

# 5.5 Treatment Compliance

Ramucirumab/placebo, 5-FU, Irinotecan, oxaliplatin will be administered only at HCRN sites by the authorized study personnel. As a result, treatment compliance is ensured.

Version Date: 13AUG2018 Confidential Page 19 of 51

# 5.6 Concurrent Therapy

Additional concurrent chemotherapy or radiation therapy, biologic response modifiers, or other investigational agents may not be administered to subjects on this study. However, palliative radiation during the study is allowed if clinically indicated.

#### 5.7 Concomitant Medications

Medications allowed:

- Medications required for supportive care during the study (See Section 5.4)
- Medications subject requires for treatment of previous comorbidities.

# 6. Toxicity Monitoring and Dose Modifications

The NCI Common Terminology Criteria for Adverse Events CTCAE v4 will be used to grade adverse events.

Subjects enrolled in this study will be evaluated clinically and with standard laboratory tests before and at regular intervals during their participation in this study as specified in Study Calendar & Evaluations.

Subjects will be evaluated for adverse events (all grades), serious adverse events, and adverse events requiring study drug interruption or discontinuation at each study visit for the duration of their participation in the study.

# 6.1 Dose Modifications for Ramucirumab/placebo

Ramucirumab/placebo will be held for Grade  $\geq 3$  study drug related adverse events until recovery to Grade  $\leq 1$  and then resume with a dose reduction (level -1; 6 mg/kg) if site investigator evaluation relates toxicity to ramucirumab/placebo. If a second Grade  $\geq 3$  drug related adverse event is experienced and does not resolve within 2 weeks of the initial dose reduction, an additional dose reduction (level -2; 5mg/kg) will be made. If Grade  $\geq 3$  related adverse event does not resolve within 2 weeks of the second dose reduction, the subject will be taken off the trial.

Table 3. Modified dose of ramucirumab

Dose level	Ramucirumab
Starting dose	8 mg/kg
Level -1 dose reduction	6 mg/kg
Level -2 dose reduction	5 mg/kg

Version Date: 13AUG2018 Confidential Page 20 of 51

Table 4. Dosing level of ramucirumab/placebo for treatment related adverse events

Toxicity NCI	Worst Interval Toxicity	Day of Treatment
Grade (value)		
1	Maintain dose level	Continue treatment per protocol schedule.
2	Maintain dose level	Hold until resolved to grade 1 or less.
3	Reduce to dose level -1 6 mg/kg	Hold until resolved to grade 1 or less.
4	Reduce to dose level -2 5 mg/kg	Hold until resolved to grade 1 or less.

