#### 5. TREATMENT PLAN

#### 5.1 Treatment Regimen

One cycle will be equal to 28 days. The ramucirumab/placebo will be administered prior to the mFOLFIRINOX regimen. Both arms will receive mFOLFIRINOX regimen given per institutional standards (suggested administration sequence below), which will be a modification of the previously published regimen.  mFOLFIRINOX will be administered every 2 weeks. Dose modifications for all medications are outlined in Section 6:

- Arm A will receive ramucirumab administered as an intravenous infusion over 60 minutes (infusion rate should not exceed 25 mg/min), at a fixed dose of 8 mg/kg every 2 weeks.
- Arm B will receive a placebo infusion. Due to the double-blinded nature of this study, the volume of placebo will be calculated as if it were ramucirumab.
- Oxaliplatin 85 mg/m^2 over 2-4 hours
- Irinotecan 165 mg/m^2 over 90 minutes
- 5-FU 2,400 mg/m^2 as a 46-hour continuous infusion without the 5-FU bolus to decrease the risk of neutropenia.

Leucovorin is not included in this regimen since the 5-FU is administered as a continuous infusion and not in bolus form.

Version Date: 13AUG2018 Confidential Page 15 of 51

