## 11.6 Excessive Toxicity – Criteria for Stopping and Interim Safety Analysis

In case of excessive toxicity, safety-stopping rules will be used. An acceptable toxicity rate will be assumed at 0.20. The study will be stopped based on an unacceptable excessive toxicity rate of 0.40. A sequential probability ratio test will be used where a likelihood ratio of 8 in favor of an excessive toxicity rate of 0.40 (vs. 0.20) provides sufficient evidence to stop the study due to excessive toxicity. Data will be continuously reviewed for excessive toxicity and statistical analysis performed if excessive toxicity is suspected. The table below provides the minimum number of patients exhibiting excessive toxicity that will trigger statistical analysis.

Total number of treated patients	Number of Patients observed with excessive toxicity
3	≥2
4-5	≥3
6-7	≥4
8-9	≥5
10-11	≥6
12-13	≥7
14-16	≥8
17-18	≥9
19-20	≥10

Version Date: 13AUG2018 Confidential Page 41 of 51

21-23	≥11
24-25	≥12
26-28	≥13
29-30	≥14
31-33	≥15
34-35	≥16
36-38	≥17
39-40	≥18

Ramucirumab will be held for drug related adverse events Grade  $\geq 3$  until recovery to Grade  $\leq 1$  and then resumed with a lower dose level -1 (6 mg/kg). If the Grade  $\geq 3$  related adverse event does not resolve within 4 weeks of holding treatment, the subject will be taken off study treatment.

In the case of prolonged or medically concerning Grade 2 toxicity related to the chemotherapy combination, treatment will be interrupted until recovery to Grade  $\leq 1$ , at which time treatment will be resumed at the same dose. If the adverse event does not resolve in or within 2 weeks with medical intervention, then the subject will be taken off study treatment.

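### Section 6.1 is inconsistent for a second related Grade 3 or higher event: it ties a further ramucirumab/placebo reduction to non-resolution, despite its own hold until Grade 1, and counts 2 weeks from the first dose reduction

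*Combined protocol and SAP*

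**What the plan says.** Section 6.1 has three operative sentences.

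- **Sentence 1** holds ramucirumab/placebo for Grade 3 or higher "study drug related adverse events until recovery to Grade" 1 or less, "and then resume with a dose reduction (level -1; 6 mg/kg) if site investigator evaluation relates toxicity to ramucirumab/placebo".
- **Sentence 2** covers a second related Grade 3 or higher event. If it "does not resolve within 2 weeks of the initial dose reduction, an additional dose reduction (level -2; 5mg/kg) will be made".
- **Sentence 3** covers an event that persists after that. If it "does not resolve within 2 weeks of the second dose reduction, the subject will be taken off the trial".

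Table 4, in the same section, sets the dose level by grade: level -1 for Grade 3 and level -2 for Grade 4. Beside both it gives the same day-of-treatment instruction: "Hold until resolved to grade 1 or less". It makes no exception for a second event.

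The synopsis (early stopping) and Section 11.6 state the same order as sentence 1. Drug is held for a related Grade 3 or higher event until Grade 1 or less, "and then resumed with a lower dose level -1 (6 mg/kg"). Each then sets a limit counted from the hold. In the synopsis it is 3 weeks, after which the subject leaves the trial. In Section 11.6 it is 4 weeks, after which the subject leaves study treatment.

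**The concern.** Sentence 1 and Table 4 make recovery the condition for giving the drug again. Sentence 2 makes lack of recovery the condition for a dose step, and sentence 3 then waits a further 2 weeks to see whether the event resolves. A site could read this as an instruction to give a lower dose during an unresolved Grade 3 or higher event. Another site, following Table 4, would hold.

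The starting point of the limit is a separate difficulty. The initial dose reduction answered the first event, so its date has no necessary relation to the onset of the second.

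This is the general dose-modification rule for the investigational agent in a blinded, multicenter trial. At stake are subject safety, uniform handling across sites, and who is removed from the trial or from treatment and when.

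**Working it through.** The plan states no figure on this point, so there is none to reproduce. The check is mainly textual, with a sensitivity calculation for the limit.

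**1. The rules side by side**

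| Source | Order of steps | Limit | Counted from |
|---|---|---|---|
| 6.1, sentence 1 | Hold, recover to Grade 1 or less, resume at level -1 | None | n/a |
| 6.1, sentence 2 | Second event not resolved, so go to level -2 | 2 weeks | Initial dose reduction |
| 6.1, sentence 3 | Event still unresolved after level -2, so off trial | 2 weeks | Second dose reduction |
| Table 4 | Level by grade; hold to Grade 1 or less | None | n/a |
| Synopsis | Hold, recover, resume at level -1; off trial if not resolved | 3 weeks | Holding treatment |
| 11.6 | Hold, recover, resume at level -1; off study treatment if not resolved | 4 weeks | Holding treatment |

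Under sentence 1 and Table 4, a dose at a new level is given only after recovery. Under sentences 2 and 3, the level -2 reduction precedes recovery, because sentence 3 asks whether the event resolves afterwards. The proteinuria rule in 6.1.2 shows the sequence written without this difficulty: interrupt, wait for recovery, then apply level -2.

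**2. The limit**

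Set day 0 at the initial dose reduction, so the limit falls on day 14. A second event starting on day x has 14 - x days in which to resolve:

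- x = 7: 14 - 7 = 7 days remain.
- x = 14: none remain.
- x = 28: 14 - 28 = -14, so the limit expired 14 days before onset.

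Section 5.1 gives the drug "at a fixed dose of 8 mg/kg every 2 weeks", and Section 6 collects adverse events "and adverse events requiring study drug interruption or discontinuation at each study visit". Day 14 is therefore about the next scheduled infusion and assessment after the first reduced dose, subject to the visit windows and any unscheduled contact.

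**3. How many second events could be affected**

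The documents do not give the timing of second events, so everything here is assumed. Let onset of the second event be exponential with weekly rate λ = ln 2 / (median onset in weeks). Let the end of treatment be exponential with weekly rate μ = ln 2 / (median remaining weeks on treatment). Among second events that occur on treatment, the share starting more than 2 weeks after the reduction is exp(-2(λ + μ)).

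The design medians for PFS in 11.10 (6 and 9 months) serve only as a scale for remaining treatment; 2 months is added as a short case.

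- 6 months, second events rare (λ near 0): 6 × 30.4375 / 7 = 26.09 weeks; μ = 0.0266; exp(-0.053) = 0.948.
- 2 months, median onset 2 weeks: 2 × 30.4375 / 7 = 8.70 weeks; μ = 0.0797; λ = 0.3466; exp(-0.853) = 0.426.

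| Median remaining treatment | Onset 2 wk | 4 wk | 8 wk | 16 wk | Rare |
|---|---|---|---|---|---|
| 2 months | 43% | 60% | 72% | 78% | 85% |
| 6 months | 47% | 67% | 80% | 87% | 95% |
| 9 months | 48% | 68% | 81% | 89% | 97% |

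If onset is instead uniform over T weeks, the share is 1 - 2/T: 75% for T = 8, 83% for T = 12, 92% for T = 26 and 95% for T = 39.

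**4. A second event that does resolve in time**

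Sentence 2 gives no dose step for it. Table 4 goes by grade: Grade 3 leads to level -1, where a subject already reduced under sentence 1 stands; Grade 4 leads to level -2. So Table 4 names a further step only for Grade 4.

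**The case against.** The strongest defence is that sentence 2 only assigns a level. Sentence 1 holds the drug for related Grade 3 or higher events in general, and Table 4 puts a reduction and a hold next to each other, so the two can coexist. Sentence 2 says that a reduction is made, not that drug is given while the event lasts. On this reading level -2 takes effect on resumption and the hold is intact.

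That reading is possible. A reader might infer that the protocol plainly orders dosing during an unresolved event, and the text does not go that far. But the protocol does not state the milder reading either, and sentence 3 fits it poorly: if level -2 is first given after recovery to Grade 1 or less, that event cannot still be unresolved 2 weeks after the reduction. Nor does it repair the starting point of the limit.

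A second objection is that a late second event still gets an instruction, since failing the limit leads to level -2. That is correct. The limit is nevertheless empty for such events, because it no longer separates those that resolve promptly from those that do not.

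Third, several serious toxicities have rules of their own in 6.1.1, 6.1.2, 6.1.5 and 6.1.6, so the disputed sentences govern the remainder. This narrows the scope of the point but does not remove it.

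**Conclusion.** The point holds as an inconsistency in the text. For a second related Grade 3 or higher event, sentences 2 and 3 of 6.1 do not fit the hold in sentence 1 and Table 4 on a literal reading. The 2-week limit cannot be met by any second event starting more than 2 weeks after the first reduction. The synopsis and 11.6 use a different starting point and two other durations. These conclusions rest on the wording alone.

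Two stronger inferences are not supported. A reader might conclude that nearly all second events fall outside the limit. The 95% to 97% that suggests this arises only if second events are rare and remaining treatment follows the design PFS medians; other assumptions lower the share to about 43%, and the documents do not choose between them. A reader might also suppose that these events are the ones most likely to differ between arms, or that the PFS comparison is biased. The documents do not say the former, and no effect on the primary analysis has been shown.

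**What to change.** The text is wrong as written and should be corrected. The sponsor should reconcile sentences 1 to 3 of 6.1, Table 4, the synopsis and 11.6 into one consistent text that applies to both arms. It should settle:

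- whether ramucirumab/placebo is held or given while a second related Grade 3 or higher event is unresolved;
- from what date, and for how long, any resolution limit is counted, and whether failing it takes the subject off the trial or off study treatment;
- what happens to the dose level when a second event resolves within the limit, in agreement with Table 4.

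Which dose, duration or starting date is right is for the sponsor to decide; none is proposed here. The cost is amendment wording in those places, with the approvals that Section 13.5 requires from the sponsor-investigator, the drug supplier and each site's IRB. No change to sample size or to the primary analysis is involved.

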# STATISTICAL CONSIDERATIONS

We aim to test the null hypothesis of PFS at 6 months. Using a one-sided log-rank test we have estimated a sample size of 85 patients (43 in one and 42 in another arm) which will provide 80% power under a type 1 error of 20%. This is an estimation on 24 months accrual and 9 months follow up after accrual for the primary endpoint. Sample size may increase to 95 to account for a 10% drop out rate.

The primary endpoint of this clinical trial is PFS. PFS is defined as the time from enrollment to the time of progression or death. An interim analysis with Kaplan Meier method and Logrank test will be conducted after 23 subjects have been enrolled in each arm and followed up for 9 months. The trial will stop if it detects a significant difference of 3 months in PFS between the study arm-mFOLFIRINOX/RAM, as compared to the standard arm-mFOLFIRINOX at the significance level of 0.0013 according to the O'Brien-Fleming approach. Otherwise the trial will continue until the targeted sample size has been completed.

RR, PFS and OS will be reported with 95% confidence intervals. Response is defined as a complete or partial response according to CT/MRI evaluations based on RECIST 1.1 criteria. Toxicity will be graded using CTCAE v4

**Early stopping:** In the case of excessive toxicity, safety-stopping rules will be used. A grade  $\geq 3$  or adverse event that will lead to stop or termination of treatment is defined as suspected treatment related toxicity observed in the first 4 weeks of enrollment after dose modification, but excluding: nausea or vomiting and hematologic toxicities if not adequately treated. Ramucirumab will be held for drug related adverse events grade  $\geq 3$  until recovery to grade  $\leq 1$  and then resumed with a lower dose level -1 (6 mg/kg). If the grade  $\geq 3$  related adverse events does not resolve within 3 weeks of holding treatment, subject will be taken off the trial. In the case of prolonged or medically concerning grade 2 toxicity related to chemotherapy combination, treatment will be interrupted until

[figure not shown]

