	recovery to grade ≤ 1, at which time treatment will be resumed at the same dose. If the adverse event does not resolve in or within 2 weeks with medical intervention, then the subject will be taken off trial.  In case of excessive toxicity, safety-stopping rules will be used. An acceptable toxicity rate will be assumed at 0.20. The study will be stopped based on an unacceptable excessive toxicity rate of 0.40. A sequential probability ratio test will be used where a likelihood ratio of 8 in favor of an excessive toxicity rate of 0.40 (vs. 0.20) provides sufficient evidence to stop the study due to excessive toxicity. Toxicity will be continuously reviewed for excessive toxicity and statistical analysis performed if excessive toxicity is suspected.  In the interim safety analysis, the study will be closed to accrual after the first 20 subjects (10 in each arm) are analyzed, if within the first cycle of treatment n/10 subjects developed any of the following grade ≥ 3 toxicity: 2/10 febrile neutropenia, 3/10 neuropathy, 3/10 hypertensive emergency or urgency, 3/10 life threatening thromboembolic event, 2/10 GI perforation or 2/10 bleeding or hemorrhage, the regimen mFOLFIRINOX RAM will be considered toxic and the trial will stop.
TOTAL NUMBER OF SUBJECTS	N = 85 to 95
ESTIMATED ENROLLMENT PERIOD	Estimated 24 months
ESTIMATED STUDY DURATION	Estimated 33 months

Page 8 of 51

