#### 7.1.6 Follow-up

For subjects who discontinue study treatment without radiographically documented PD, the investigative sites will continue to evaluate tumor response every 8 weeks by the same method used at baseline and throughout the study until time of disease progression, death or until study completion, except when not feasible in the opinion of the site investigator due to subject's clinical status.

Version Date: 13AUG2018 Confidential Page 28 of 51

After the subject has documented PD, radiologic assessments are no longer required and the subject will be followed up every 8 weeks (+/- 7 days) until the subject's death or study completion, whichever is earlier.

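### For unresolved toxicity, the synopsis and 6.1 remove the subject from the trial while 11.6 only stops study treatment; removal from the trial may be read as ending PFS and OS follow-up

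*Combined protocol and SAP*

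**What the plan says.** Three places in the combined protocol and SAP deal with toxicity that does not resolve.

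- **Synopsis, Statistical Considerations (early stopping).** If a related grade 3 or higher event "does not resolve within 3 weeks of holding treatment, subject will be taken off the trial". If prolonged or medically concerning grade 2 toxicity from the chemotherapy combination has not cleared in two weeks, "then the subject will be taken off trial".
- **Section 6.1 (ramucirumab/placebo).** If the grade 3 or higher event has not cleared two weeks after the second dose reduction, "the subject will be taken off the trial".
- **Section 11.6.** If the grade 3 or higher event "does not resolve within 4 weeks of holding treatment, the subject will be taken off study treatment". If the grade 2 event "does not resolve in or within 2 weeks with medical intervention, then the subject will be taken off study treatment".

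Section 7.1.6 sets the follow-up: "For subjects who discontinue study treatment without radiographically documented PD, the investigative sites will continue to evaluate tumor response every 8 weeks". This runs to progression, death or study completion, and subjects with documented progression are then followed for survival. Note 9 of the study calendar says the same. Section 6.4 deals separately with leaving the study as opposed to leaving therapy. Section 8.3.7 censors PFS at the last disease evaluation for subjects without progression, and 8.3.8 gives no censoring rule for OS.

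**The concern.** The protocol gives two statuses for a subject whose toxicity persists, and they are not interchangeable. Under 6.4 a subject who leaves the study has a final evaluation, and the section provides for removal because of an adverse event. A site that takes 6.1 at its word therefore has a matching procedure that ends scans and survival contacts.

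The primary analysis in 11.4 is a log-rank test in the ITT dataset, and 11.9 wants subjects followed whatever their compliance. If follow-up stops at removal, later progressions and deaths are never observed and cannot be recovered at analysis. Losing them costs power. If removal is also more frequent in one arm and happens to patients with a different outlook, the censoring is informative and the hazard ratio moves.

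**Working it through.** **1. The passages side by side**

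| Rule | Trigger | Consequence |
|---|---|---|
| Synopsis, grade 3+ | 3 weeks of holding | leaves trial |
| 11.6, grade 3+ | 4 weeks of holding | leaves study treatment |
| 6.1, grade 3+ | 2 weeks after second dose reduction | leaves trial |
| Synopsis, grade 2 | 2 weeks with intervention | leaves trial |
| 11.6, grade 2 | 2 weeks with intervention | leaves study treatment |

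The grade 2 rows are the cleanest comparison: same trigger, same window, different consequence. The grade 3+ rows also differ in trigger and window.

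**2. The plan's own figure (11.10)**

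Inputs: medians 6 and 9 months, HR 0.6667, one-sided alpha 0.20, 43 control and 42 treatment subjects, 24 months of accrual plus 9 of follow-up. With exponential PFS and uniform accrual, P(event) = 1 − [exp(−9λ) − exp(−33λ)] / (24λ).

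- Control: λ = ln 2/6 = 0.1155, P = 0.880.
- Ramucirumab: λ = ln 2/9 = 0.0770, P = 0.772.
- Expected events: 43 × 0.880 + 42 × 0.772 = 70.3.
- Power (Schoenfeld): Φ(√70.3 × 0.4055/2 − 0.8416) = Φ(0.858) = 0.805. The Freedman version gives 0.798. The plan states 0.8014, so its figure is reproduced.

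**3. Lost events if removal ends follow-up**

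Assumption (not in the documents): 15% of each arm removed, uniformly over months 1 to 4, with no link to prognosis. The chance of progressing before the removal time is 1 − [exp(−λ) − exp(−4λ)] / (3λ), which is 0.247 for control and 0.173 for ramucirumab.

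- Events lost: 0.15 × [43 × (0.880 − 0.247) + 42 × (0.772 − 0.173)] = 0.15 × 52.4 = 7.9.
- Events left: 70.3 − 7.9 = 62.4.
- Power: Φ(√62.4 × 0.4055/2 − 0.8416) = Φ(0.760) = 0.776, a drop of about 0.03.

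Two simulations of this setting also gave about 62 events, with power falling from 0.795 to 0.759 (6,000 trials) and from 0.81 to 0.78 (5,000 trials).

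**4. Hazard ratio if removal differs by arm**

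These are 3,000 simulated trials per setting with 43 + 42 subjects, a true HR of 0.667 before any added hazard, and a one-step HR estimate. Removal rates, removal at months 1 to 4, and the change in hazard from the removal time are all assumed. The last two columns give the rejection rate when ramucirumab has no direct effect.

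| Removed A / B | Hazard after removal | HR followed | HR censored | Rejection followed | Rejection censored |
|---|---|---|---|---|---|
| 20% / 5% | ×1 | 0.661 | 0.667 | 0.185 | 0.201 |
| 10% / 5% | ×2 | 0.678 | 0.662 | 0.183 | 0.196 |
| 20% / 10% | ×2 | 0.694 | 0.663 | 0.144 | 0.202 |
| 20% / 5% | ×2 | 0.713 | 0.662 | 0.141 | 0.199 |

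The Monte Carlo error of a rejection rate near 0.20 is √(0.2 × 0.8/3000) = 0.007. With no link to prognosis (first row), the 0.006 difference in HR is not evidence of bias. In that row the cost is events (70.3 to 63.9) and power (0.80 to 0.77). If the hazard is doubled throughout rather than from removal, 20% / 5% gives HR 0.73 followed and 0.69 censored, with rejection 0.11 and about 0.15-0.16.

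**The case against.** A reader might infer that the synopsis and 6.1 do end follow-up and so do bias the trial toward ramucirumab. The documents do not support that.

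- No passage says follow-up stops. Section 6.3 opens by describing toxicity stops as discontinuation from therapy. Section 7.1.4 lists unacceptable toxicity among the reasons for stopping protocol therapy.
- Section 6.1.1, directly below the rule in 6.1, keeps subjects with uncontrolled severe hypertension in follow-up under Section 7. Note 9, 7.1.6 and 11.9 point the same way. Section 6.4 is framed mainly around the subject's own decision.
- No removal rates by arm are given. The grade 2 rule concerns chemotherapy toxicity, which both arms can have, and removal under 6.1 needs failure after a second dose reduction. That 20% of Arm A would be removed by months 1 to 4 is purely an assumption.
- Section 11.10 allows N to rise to 95 for dropout. At that size the 62 events would scale to 62 × 95/85 = 69.

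Most of this stands, and the intent was probably to keep following these subjects. It does not remove the conflict. Section 6.3 attaches its follow-up instruction to a list given in addition to toxicity stops. Section 7.1.6 speaks only of stopping treatment. The general rule in 6.1 lacks the follow-up sentence that 6.1.1 has. The increase to 95 is optional, is meant for dropout in general, and cannot correct a bias.

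**Conclusion.** The contradiction is certain; its consequence is conditional. If a site reads the synopsis or 6.1 as study removal, PFS events are lost, and so is OS follow-up. With 15% removed per arm the loss is about 8 of 70 events and about 0.03 of power.

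Bias needs two further conditions: removal that differs by arm and removal that is related to prognosis. Under the assumed rates the HR shift is none when removal is unrelated to prognosis. With the hazard doubled it is about 0.02 at 10% against 5% removed, and about 0.04-0.05 at 20% against 5%.

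A reader might also infer an inflated type I error. The runs do not show this: with no direct drug effect, rejection after censoring is about 0.15 to 0.21 against the nominal 0.20. What censoring does is hide a disadvantage that the ITT analysis would count. The sample size in 11.10 is unaffected. The case for the fix rests on the contradiction with the plan's own ITT principle and does not depend on any simulated figure.

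**What to change.** Reconcile the two synopsis rules and 6.1 with 11.6 on the subject's status. State once that any subject who stops for toxicity remains on study and is followed for progression and survival under 7.1.6. Reserve the wording about leaving the study for withdrawal under 6.4.

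In the same amendment the sponsor should reconcile the grade 3 or higher triggers and windows (3 weeks of holding, 4 weeks of holding, 2 weeks after the second dose reduction) and say which study drugs each rule covers. Those are clinical decisions, and none is proposed here.

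The cost is three wording changes and one sentence, through the amendment route in 13.5. The scans and contacts are already in the calendar, and sample size, alpha and analysis do not change.
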